4.11. End of Treatment (EOT)

All subjects will return to the study site 30 days (\pm 7 days) after the last dose of study drug (or within 7 days prior to initiation of a new anti-cancer treatment, whichever comes first) for an EOT evaluation. Procedures and assessments performed at this visit and beyond should follow the respective guidelines described in **Sections 4.12 and 9** as appropriate.

4.12. Duration of Follow Up

4.12.1. Safety Follow-up

Subjects who discontinue treatment should be contacted by telephone or email at 100 days (+ 14 day reporting window) from their last dose of study drug or within 7 days before initiation of a new antineoplastic treatment (whichever comes first) to assess for treatment related toxicities. In addition, all SAEs occurring during this time should be reported as well.

Subjects who are discontinued from the study treatment due to an unacceptable drug-related AE will be monitored for safety until the resolution of the AE to \leq grade 1 or stabilization or until initiation of a new therapy for their cancer, whichever occurs first.

4.12.2. Clinical Follow-up

All enrolled subjects who discontinue treatment without disease progression will enter the clinical follow-up portion of the trial. Subjects will begin the clinical follow-up period after they complete the EOT visit. Clinical follow-up visits will occur every 12 weeks (\pm 2 weeks) until: 1) start of a new antineoplastic therapy (information of the new cancer therapy will be collected), 2) disease progression, 3) death, 4) withdrawal of consent, or 5) study closure, whichever occurs first. Refer to **Section 9** for the schedule of assessments that should be performed at each visit. After disease progression or start of a new antineoplastic therapy, subjects will enter the survival follow-up portion of the trial (**Section 4.12.3**).

4.12.3. Survival Follow-up

Subjects who discontinue treatment and have disease progression will enter the survival follow-up portion of the trial. Subjects should be contacted every 12 weeks (\pm 2 weeks) to monitor overall survival. Information of other cancer therapies after discontinuation from the study treatment will be collected as well.

5. DOSING DELAYS/DOSE MODIFICATIONS

5.1. Dose Modifications

Subjects will be monitored continuously for AEs while on study drug. Subjects will be instructed to notify their physician immediately for any and all AEs. Dose escalations or reductions of cemiplimab or plerixafor will not be allowed.

5.2. Dose Delays

In some cases, the natural history of select AEs associated with immunotherapy can differ from and be more severe than AEs caused by other therapeutic classes. Early recognition and management may mitigate severe toxicity.

Guidance for Investigators is provided in the current cemiplimab and plerixafor Investigator's Brochures. Additionally, management algorithms have been developed to assist Investigators with select toxicities and can be found in the NCCN's guidelines for the management of immunotherapy-related toxicities.

Subjects who experience the following must have all study drugs held:

- Select drug-related AEs and drug-related laboratory abnormalities:
 - Grade \geq 2 pneumonitis
 - AST/ALT $>$ 3 x ULN
 - Bilirubin $>$ 1.5 x ULN (except subjects with Gilbert Syndrome, who can have total bilirubin $<$ 3.0 mg/dL)
 - Creatinine $>$ 1.5 x ULN
 - Grade \geq 3 diarrhea or colitis
 - Grade \geq 2 neurological AE
- Any AE, laboratory abnormality, or intercurrent illness which, in the judgment of the investigator, warrants delaying the dose of study drug.

Subjects not meeting guidelines for permanent discontinuation will be permitted to resume therapy when the treatment-related AE(s) resolve to grade \leq 1 or baseline value, with the following exceptions:

- If the toxicity resolves to \leq Grade 1 or baseline $>$ 6 weeks after last dose, but the subject does not otherwise meet criteria for permanent discontinuation, and the Investigator

believes that the subject is deriving clinical benefit, then the subject may be eligible to resume the study drugs following the approval of the Protocol Chair.

- Subjects with grade 4 drug-related amylase and/or lipase increase that is not associated with symptoms or clinical manifestations of pancreatitis can continue on therapy.
- Subjects may resume treatment in the presence of Grade 2 fatigue.
- Subjects with baseline normal or grade 1 AST, ALT or total bilirubin who require dose delays for reasons other than a drug-related hepatic event may resume treatment in the presence of grade 2 AST, ALT or total bilirubin elevation.
- Subjects who require dose delays for drug-related elevations in AST, ALT, or total bilirubin may resume treatment when these values have returned to their baseline CTCAE grade or normal, provided the criteria for permanent discontinuation are not met.
- Treatment-related endocrinopathies adequately controlled with only physiologic hormone replacement may resume treatment.

Subjects eligible to resume study drug will resume study drug at the treatment visit following their last received study drug dose.

The on treatment tumor assessments (i.e., CT/MRI, positron emission tomography [PET], etc.) will continue on an every 9-week schedule relative to the subject's first dose regardless of any treatment delay incurred. Subjects who are required to permanently discontinue both study drugs are listed in **Section 4.10**.

6. ADVERSE EVENTS: LIST AND REPORTING REQUIREMENTS

This study will use the descriptions and grading scales found in the revised CTCAE version 5.0 for AE reporting.

Information about all AEs, whether volunteered by the subject, discovered by investigator questioning, or detected through physical examination, laboratory test or other means, will be collected, recorded, and followed as appropriate.

6.1. Definitions

6.1.1. Adverse Event

An AE is defined as any undesirable sign, symptom or medical condition occurring after starting the study drug (or therapy) even if the event is not considered to be related to the study. An undesirable medical condition can be symptoms (e.g., nausea, chest pain), signs (e.g., tachycardia, enlarged liver) or the abnormal results of an investigation (e.g., laboratory findings, electrocardiogram). Medical conditions/diseases present before starting the study treatment are only considered AEs if they worsen after starting the study treatment (any procedures specified in the protocol). New medical conditions / diseases occurring before starting the study treatment but after signing the informed consent form will not be recorded as AEs. Additionally, expected progression of the disease being studied will not be recorded as an adverse event.

Laboratory abnormalities: Laboratory abnormalities present at the screening visit will be recorded as pre-treatment signs and symptoms. After study treatment administration, all grade 3 and 4 clinical laboratory results that represent an increase in severity from baseline will be reported as AEs. A grade 1 or 2 clinical laboratory abnormality should be reported as an AE only if it is considered clinically significant by the investigator (induce clinical signs or symptoms or require corrective therapy), meets the definition of an SAE, or requires the participant to have study drug discontinued or interrupted. It is expected that wherever possible, the clinical rather than laboratory term would be used by the reporting investigator (e.g., anemia versus low hemoglobin value).

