3. PATIENT SELECTION

3.1. Eligibility Criteria

3.1.1. Age \geq 18 years.

3.1.2. ECOG performance status of 0-1 (**Appendix A**).

3.1.3. Have histologically- or cytologically-proven ductal adenocarcinoma of the pancreas.

- 3.1.4. Have metastatic disease.
- 3.1.5. Have documented radiographic disease progression at the time of study enrollment, after previous systemic chemotherapy given in a neoadjuvant, adjuvant, locally advanced or metastatic setting.
- 3.1.6. Presence of at least one lesion with measurable disease as defined by 10 mm in longest diameter for a soft tissue lesions or 15 mm in short axis for a lymph node by RECIST 1.1.
- 3.1.7. Patient's acceptance to have a tumor biopsy of an accessible lesion at baseline and on treatment.
- 3.1.8. Life expectancy of greater than 3 months.

- 3.1.9. Adequate organ and marrow function as defined below:

- Leukocytes $\geq 3,000/\text{mcL}$
- Absolute neutrophil count $\geq 1,000/\text{mcL}$
- Platelets $\geq 90 \times 10^3/\text{uL}$
- Hemoglobin $\geq 8.0 \text{ g/dL}$
- Total bilirubin ≤ 1.5 upper limit of normal (ULN) except subjects with Gilbert Syndrome, who can have total bilirubin $< 3.0 \text{ mg/dL}$
- AST(SGOT) and ALT(SGPT) $\leq 3.0 \times \text{ULN}$
- Alkaline phosphatase $\leq 5.0 \times \text{ULN}$
- Creatinine $\leq 1.5 \times \text{ULN}$ or creatinine clearance (CrCl) $\geq 40 \text{ mL/min}$ (if using the Cockcroft-Gault formula below):

$$\text{Female CrCl} = \frac{(140 - \text{age in years}) \times \text{weight in kg} \times 0.85}{72 \times \text{serum creatinine in mg/dL}}$$

$$\text{Male CrCl} = \frac{(140 - \text{age in years}) \times \text{weight in kg} \times 1.00}{72 \times \text{serum creatinine in mg/dL}}$$

- Albumin $\geq 3.0 \text{ g/dL}$

- 3.1.10. Women of childbearing potential (WOCBP) must have a negative serum pregnancy test (minimum sensitivity 25 IU/L or equivalent units of human chorionic gonadotropin [HCG]). WOCBP is defined in **Section 4.8**. NOTE: If a patient has a positive or indeterminate serum or urine pregnancy test, then an ultrasound must be done to rule out pregnancy to enroll on trial.

- WOCBP must agree to follow instructions for method(s) of contraception from the time of enrollment for the duration of treatment with study drug(s) plus 5 half-lives of study drug(s) plus 4 weeks (duration of ovulatory cycle) for a total of 5 months post treatment completion.

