6.5. Reporting

6.5.1. Adverse Events (AEs) and Serious Adverse Events (SAEs)

All AEs (both expected and unexpected) occurring from the first dose of study drug will be captured on the appropriate study-specific case report forms (CRFs).

All AEs (both related and unrelated) will be captured on the appropriate study-specific CRFs. All AEs experienced by subjects will be collected and reported from the first dose of the investigational agent, throughout the study, and will be followed for 28 days after last dose of study drug unless related to the investigational agent.

Subjects who experience a grade 3 or higher cemiplimab or plerixafor-related AE should be discussed with the Protocol Chair.

Report AEs to the Protocol Chair within 24 hours once identified as an unacceptable toxicity (defined in Section 4.7).

[name] (Protocol Chair): [REDACTED]

Report AESIs to the Protocol Chair and Sanofi within 24 hours once identified (defined in Section 6.1.3) using the form found in Appendix E.

[name] (Protocol Chair): [REDACTED]

Sanofi: [REDACTED]

Regeneron: [REDACTED]

All SAEs (including deaths) occurring from the first dose of study drug, throughout the study, and 100 days (+14 day reporting window) after the last dose of study drug or before initiation of a new antineoplastic treatment (whichever comes first) must be reported. All SAEs that the investigator considers related to the study drug occurring after the follow-up periods must be reported.

SAEs will be reported promptly to the Protocol Chair and Sanofi within 24 hours of recognition of the adverse event using the form found in **Appendix D**. If this falls on a weekend or holiday, an email notification is acceptable but must be followed by an SAE reporting form on the next business day.

SAE reports and any other relevant safety information are to be sent to:

[name] (Protocol Chair): [REDACTED]

Sanofi: [REDACTED]

Regeneron: [REDACTED]

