- 18: Whole blood for PBMC, plasma, and serum will be collected at baseline (any time prior to the first dose after eligibility is met), Cycle 1 Days 8 and 15, Cycle 2 Days 1 and 8, Cycle 4 Day 1, and Cycle 7 Day 1. Plasma and serum samples will also be collected on Day 8 of Cycles 4 and 7. Additional optional blood samples may be obtained later in the course of study treatment if patients have a response of interest. Detailed instructions for sample collection, processing, and shipment are provided in the Laboratory Manual.
- 19: Tumor biopsies to be taken (4-6 cores per time point, if a subject's tumor is thought to be reasonably safe and easy to biopsy) at the following timepoints: 1. Baseline (any time prior to the first dose after eligibility is met), 2. Prior to dosing on either Cycle 1 Day 8 (-1 day) or Cycle 2 Day 1 (-3 day) for alternating patients, and 3. Optional biopsy may be obtained at the time of disease progression or if there is a response of interest. Fine needle aspiration will not be acceptable. Detailed instructions for tissue collection, processing, and shipment are provided in the Laboratory Manual.
- 20: Cycle 1 Day 1 evaluations do not need to be repeated if they were conducted within 3 days of the pre-study evaluations.
- 21: EOT visit will occur 30 (\pm 7) days after the final dose (or within 7 days prior to initiation of a new anti-cancer treatment, whichever comes first). NOTE: CT scan assessment at EOT will occur 30 days (\pm 4 weeks) after the final dose. If the EOT visit occurs early, an assessment for AEs should be made by telephone or email on day 30 (\pm 1) after last study dose.

- 22: Subjects who discontinue treatment should be contacted by telephone or email at 100 days (+ 14 day reporting window) from their last dose of study drug or within 7 days before initiation of a new antineoplastic treatment (whichever comes first) to assess for treatment related toxicities. In addition, related SAEs occurring during this time should be reported as well.
- 23: Subjects who discontinue treatment without disease progression will enter the clinical follow-up portion of the trial (**Section 4.12.2**). Clinical follow-up visits will occur every 12 weeks (\pm 2 weeks) until progression. After disease progression, subjects will enter the survival follow-up portion of the trial.

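### Adverse event and SAE capture starts at the first dose, so Section 6 gives no recording or reporting route for complications of the protocol-specified pre-dose core biopsy

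*Combined protocol and SAP*

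**What the plan says.** **The biopsy.** Section 3.1.7 makes the patient's "acceptance to have a tumor biopsy of an accessible lesion at baseline and on treatment" a condition of entry. Footnote 19 of the Section 9 calendar specifies 4-6 cores per time point and rules out fine needle aspiration. It sets the first two time points as "Baseline (any time prior to the first dose after eligibility is met), 2. Prior to dosing on either Cycle 1 Day 8", with Cycle 2 Day 1 as the alternative for the second. The same footnote makes the biopsy conditional on the tumor being safe and easy enough to reach, and footnote 26 leaves research samples to the PI's discretion. Sections 1.3.4 and 8.1 give its purpose as correlative research.

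**The capture window.** Section 6.1.1 ties the definition of an adverse event to the period after study drug starts. It then says that new conditions "occurring before starting the study treatment but after signing the informed consent form will not be recorded as AEs". Section 6.5.1 states "All AEs experienced by subjects will be collected and reported from the first dose of the investigational agent", and gives the SAE window separately: "All SAEs (including deaths) occurring from the first dose of study drug, throughout the study". In the calendar, the concomitant medication and adverse event row is blank at screening and begins on Day 1.

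**The analysis sets.** Section 12.2 limits the safety analysis to treated subjects. Section 10.1 replaces subjects who leave before their first dose and excludes them from the primary efficacy analysis.

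**The concern.** A multi-core biopsy of a metastatic or pancreatic lesion is the most invasive thing the protocol asks for before dosing, and it is done for research. The capture rules exclude exactly the interval in which it takes place. Section 6.1.1, Section 6.5.1 and the calendar all use the same start point, so this is a stated rule and not a drafting slip in one sentence.

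What is at stake is the record of harm from a research procedure. A complication that prevents dosing would appear in no planned safety table, because the patient is replaced and was never treated. A complication in a patient who is still dosed would not be recorded as an adverse event unless it worsened after dosing began.

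**Working it through.** No figure in the plan describes this point, so there is nothing to reproduce. The check is mainly textual.

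**Step 1: follow a baseline biopsy complication through the rules.**

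| Situation | Where the rules put it |
|---|---|
| New event after the biopsy, before first dose | Not an AE (6.1.1); before the AE window opens (6.5.1) |
| Same event, serious or fatal | Before the SAE window opens (6.5.1) |
| Event prevents dosing | Patient replaced (10.1); outside the treated safety set (12.2) |
| Event occurs, patient is still dosed | Patient stays in both sets; the event counts as an AE only if it worsens after dosing (6.1.1) |
| Event from the on-treatment biopsy | After first dose, so captured (6.5.1) |

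**Step 2: look for another route in the protocol.** Screening laboratory abnormalities are noted as pre-treatment signs and symptoms (6.1.1), but that is not AE or SAE reporting. Section 6.2 assesses relationship to study drug only. The SAE form in Appendix D offers plerixafor, cemiplimab and underlying disease as causes, with no entry for a study procedure. No section states a pre-dose reporting route.

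**Step 3: count the biopsies.** Section 12.1 plans 21 patients in stage one and 18 more in stage two.

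- Both stages enrol: 21 + 18 = 39 baseline biopsies in evaluable patients, as a maximum.
- Stop after stage one: 21.
- Expected number at the null response rate, using the stated early-stopping probability of 0.51: 21 + 18 × (1 − 0.51) = 29.8, or about 30. This ignores the toxicity rule, which can halt accrual from the sixth patient.

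Biopsies not done under footnotes 19 and 26 lower these counts. Biopsies in replaced or never-dosed patients raise them. With one pre-dose and one on-treatment biopsy planned per patient, the uncaptured share is 1/2 of the planned total.

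**Step 4: illustrate the size.** The documents give no complication rate, so the rate p is assumed. The expected number of complications is n × p. The chance of at least one is 1 − (1 − p)^n, treating patients as independent.

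| Assumed rate | n = 21: expected; chance of at least one | n = 39: expected; chance of at least one |
|---|---|---|
| 1% | 0.21; 19% | 0.39; 32% |
| 2% | 0.42; 35% | 0.78; 55% |
| 5% | 1.05; 66% | 1.95; 86% |
| 10% | 2.10; 89% | 3.90; 98% |

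These rows cover complications of any severity. Only those arising before the first dose fall in the gap.

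**The case against.** **Starting at first dose is a legitimate convention.** It is applied consistently, and the trial's decisions do not depend on pre-dose events. The response rule in 12.1, the stopping rule in 4.7 and 12.2, and the drug-related toxicity endpoints in 10.2 would be the same either way. All of that stands. It limits the point to procedural safety and does not supply the missing route.

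**Section 6.1.1 contains a parenthesis that mentions procedures specified in the protocol.** It could be read as widening what counts as study treatment. But it sits in the sentence on worsening of pre-existing conditions, and Section 6.5.1 fixes both windows at the first dose of drug. At most it is an ambiguity to tidy up in the same edit.

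**Other oversight exists.** Section 11.2 provides safety meetings, 11.3 provides PI review, external monitoring and a Safety Monitoring Committee, and 6.5.7 sends SAEs to the IRB under institutional guidelines. A reader might infer that the committee can have no sight of biopsy risk, or that a serious biopsy harm would go unreported everywhere. The documents support neither inference. On-treatment biopsies use the same number of cores and their harms are captured. The meetings could surface an event, and the institutional guidelines are not available to check. What can be said is that the protocol itself states no pre-dose route.

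**The scale is easy to overstate.** A reader might take 39 as a minimum, but Section 12.1 gives it as the maximum sample size, and biopsies are conditional. A reader might also infer that every patient harmed before dosing leaves both analysis sets. Under 10.1 and 12.2 that follows only when the harm prevents dosing.

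**Conclusion.** The point holds for Section 6: complications of the baseline core biopsy that arise before the first dose are neither recorded as AEs nor reportable as SAEs under the protocol's own rules. The exposure is up to 39 baseline biopsies in evaluable patients, or 21 if stage one stops the trial, adjusted down for biopsies not done and up for replaced or never-dosed patients. The number of harms is unknown, and the percentages shown rest entirely on assumed rates.

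The conclusion assumes that no pre-dose reporting route exists outside the text available here, such as in the institutional IRB guidelines. If one does, the protocol should refer to it. The primary inference is untouched. The change should be made because it closes a gap in participant safety reporting at little cost.

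**What to change.** Five linked edits are needed, because changing Section 6.1.1 and 6.5.1 alone would leave these events with no causality field and no analysis population.

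1. **6.1.1 and 6.5.1:** state that AEs and SAEs attributed to protocol-required procedures, including the baseline research biopsy, are recorded and reported from informed consent (or from the first protocol procedure). Clarify the parenthesis in 6.1.1 at the same time.
2. **6.2:** add study procedure as a causality category alongside study drug.
3. **Appendix D:** add the same category to the SAE form.
4. **Section 9:** add a procedure-related adverse event mark at screening.
5. **12.2:** list these events separately for all consented patients who had the procedure, including those never dosed, and keep them out of the drug-toxicity tables.

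Unrelated pre-dose events can stay outside the AE definition. The cost is small edits to the protocol and forms and a few extra CRF entries between consent and first dose. Drug-related toxicity endpoints, stopping rules, the sample size and the treated-subject safety set do not change.

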6.1.2. Serious Adverse Event

A SAE is an undesirable sign, symptom or medical condition which:

- Results in death
- Is life threatening (defined as an event in which the subject was at risk of death at the time of the event; it does not refer to an event which hypothetically might have caused death if it were more severe)
- Requires inpatient hospitalization or causes prolongation of existing hospitalization (see note below for exceptions) for >24 hours
- Results in persistent or significant disability/incapacity
- Is a congenital anomaly/birth defect (note: reports of congenital anomalies/birth defects must also be reported on the Pregnancy Form)
- Is an important medical event (defined as a medical event(s) that may not be immediately life-threatening or result in death or hospitalization but, based upon appropriate medical and scientific judgment, may jeopardize the subject or may require intervention [e.g., medical, surgical] to prevent one of the other serious outcomes listed in the definition above.) Examples of such events include, but are not limited to, intensive treatment in an emergency room or at home for allergic bronchospasm; blood dyscrasias or convulsions that do not result in hospitalization.)
- Potential drug induced liver injury (DILI) is also considered an important medical event.
- Suspected transmission of an infectious agent (e.g., pathogenic or nonpathogenic) via the study drug is an SAE.
- Is a new cancer (that is not a condition of the study)
- Is associated with an overdose
- Is a pregnancy or pregnancy outcome of spontaneous abortion, missed abortion, benign hydatidiform mole, blighted ovum, fetal death, intrauterine death, miscarriage, or stillbirth.

Events **not** considered to be SAEs are hospitalizations for:

- a visit to the emergency room or other hospital department <24 hours, that does not result in admission (unless considered an important medical or life-threatening event)

- Admissions as per protocol for a planned medical/surgical procedure or to facilitate a procedure
- Routine health assessment requiring admission for baseline/trending of health status (e.g., routine colonoscopy)
- Medical/surgical admission for purpose other than remedying ill health state and was planned prior to entry into the study. Appropriate documentation is required in these cases.
- Admission encountered for another life circumstance that carries no bearing on health status and requires no medical/surgical intervention (e.g., lack of housing, economic inadequacy, care-giver respite, family circumstances, administrative).

